7.2 Safety Analysis

7.2.1 Adverse events

Adverse event (AE) data is described according to the current version of MedDRA and then statistically analyzed.

SAEs within 90 days and 360 days post-procedure and the incidence of serious surgery-related complications within 30 days after surgery are summarized. The incidence of AEs is recorded as 1 case if multiple AEs occur in one patient or the same AE occurs frequently in one patient.

AEs will be summarized by system organ class (SOC) and preferred term (PT) in a frequency table. The incidence is calculated by systems and symptoms/signs (count of cases: the number of subjects with at least one AE).

Severity of AEs: When the same subject has the same AE several times, the most serious one is used to analyze the severity of the AE.

A list of subjects experiencing AEs will be provided.

7.2.2 Death

Mortality within 90 days and 360 days post-procedure is summarized, and a list of cases is provided.

7.2.3 Concomitant medication (during the study)

Summarize the usage of concomitant medication during the study (including any changes in concomitant medication during screening, new concomitant medication after screening, and drugs for treating AEs), and the frequency of use of each drug.

7.3 Efficacy Analysis

7.3.1 Primary efficacy analysis

Summarize the incidence of the primary endpoint event.

Primary endpoint event: incidence of recurrence (surgery group) or progression (drug therapy

group) of SDH within 90 days post-procedure

Hematoma recurrence refers that the maximum thickness of hematoma exceeding 10 mm, combined with neurological symptoms, or the patient needs to undergo re-operation (surgery group);

Symptomatic CSDH progression refers that the maximum thickness of hematoma increasing by more than 3 mm compared with baseline, or the patient requires operation (drug therapy group).

Note: The primary endpoint event is considered to have been met for any patient who died from any cause within 90 days post-procedure.

Cochran-Mantel-Haenszel (CMH) chi-square analysis will be used for primary endpoints. The difference in event incidence between the two groups and its 95% confidence interval will be calculated. The Kaplan-Meier (KM) method is further used to estimate the incidence of primary endpoint events and its 95% confidence interval.

SAS code to be used in CMH analysis is as follows:

```
ods output CMH=CMH_out;  
  
proc freq data=FatComp order=data;  
  
tables Layer*Exposure*Response /CMH ALPHA=0.05;  
  
weight count;  
  
output out=cmh_ci cmh;  
  
run;
```

Sas code to be used for KM estimation is as follows:

```
proc lifetest data=TTE alpha=0.05;  
  
time avalm*cnsr(1);  
  
strata /group=trtg;  
  
ods output Quartiles = Quartiles
```

```
ProductLimitEstimates=Estimates;  
run;
```

7.3.2 Secondary efficacy analyses

Summarize the following indicators:

- Recurrence or progression rate of SDH at 360 days post-procedure
- Success rate of target blood vessel embolization (MMA trunk and branch vessels) on DSA imaging
- Change in hematoma thickness on CT/MRI at 90 days post-procedure
- Change in hematoma volume at 90 days post-procedure
- Change in midline shift on CT/MRI at 90 days post-procedure
- Change in mRS score at 90 days and 360 days post-procedure
- Proportion of patients with mRS ≤ 2 at 90 days and 360 days post-procedure
- Proportion of patients with mRS ≤ 3 at 90 days and 360 days post-procedure
- Quality of life evaluated with EQ-5D Scale at 90 days and 360 days post-procedure
- Total hospital length of stay, number of re-hospitalizations, destination for rehabilitation after discharge (home vs. rehabilitation hospital) and total hospitalization expenses

Same as primary endpoint analysis, Chi-square test (qualitative indicator) or t-test (quantitative indicators) is used for inter-group comparison in secondary endpoint analysis.

For time event endpoints, such as incidence of recurrence or progression of SDH at 360 days post-procedure, the KM method will be used.

7.3.3 Sub-Group analysis

In the evaluation of both primary and secondary outcomes, pre-specified subgroup analyses were conducted, focusing on distinctions between patients undergoing burr-hole drainage and those receiving optimal medical management. For safety assessments, the analysis encompasses all patients who were randomized and subsequently underwent the study

treatment.

8. Data Management

8.1 Filing of Case Report Form

The design of the Case Report Form (CRF) shall guarantee the collection of all data which are specified in the study protocol and meet the needs of statistical analysis. Electronic Case Report Form (eCRF) is an electronic form of CRF, which is used to record the data of each subject during the trial. The eCRFs must be filled in and completed for all included cases.

Electronic Data Capture System (EDC) for clinical trials is adopted for data collection management. The clinical trial investigator or Clinical Research Coordinator (CRC) shall fill in the eCRF accurately, timely, completely, and standardly according to CRF filing instructions.

8.2 Data Verification and Query

In order to ensure the integrity, consistency, and accuracy of data, automatic logic verification and manual logic verification are adopted. The EDC system performs real-time automatic logic verification on the filled data, such as the range and logical relationship of data values. The data administrator will send a manual Query in EDC.

8.3 Database Locking

After completing all data filling and query clearing, the PI, statistical analyst, Sponsor representative, clinical research associate (CRA) representative, and data administrator complete the final definition and judgment of the analysis population, and approve database locking in writing, and then the data administrator locks the database.

Generally, the locked database cannot be unlocked. If unlocking is needed, the unlocking conditions and procedures must conform to the corresponding SOP, and the unlocking process must be carefully controlled and recorded.

9. Ethical Protection and Informed Consent of Clinical Study

9.1 Ethical Considerations

The clinical study shall be conducted in compliance with the codes of ethics set forth in the *Declaration of Helsinki* by World Medical Association and *Good Clinical Practice for Medical*

Device Clinical Trials. Before the study begins, the Ethics Committee (EC) shall strictly deliberate the study protocol and related documents from the perspective of protecting the rights and interests of subjects, and the study can be implemented only after obtaining the written approval of the EC. All parties involved in the study shall bear corresponding ethical responsibilities according to their respective responsibilities in the study.

9.2 Approval of Study Protocol

Before the clinical study, the investigators need to submit the clinical study protocol, ICF and other related documents to the EC of hospitals where the clinical study site is located. The clinical study can only be started after approved by the EC. Any amendment to the study protocol must be approved by the EC before it can be implemented.

9.3 Informed Consent Process and Informed Consent Form

Before including a subject, the investigator must explain details of the clinical study to the subject:

The subject voluntarily participates in the clinical study and has the right to withdraw from the clinical study at any stage;

The personal data of the subject will be kept confidential. The EC, the drug regulatory authority and the implementer may consult the information of the subject, but shall not disclose the contents;

During the clinical study, the medical institution has the obligation to provide the subject with information related to the clinical study;

The subject is informed about the contents, objectives, and possible AEs of this study, and can only be included after fully understanding this study and signing the ICF;

The ICF is jointly signed by the investigator and the subject in duplicate, each copy for each party.

10. Provisions on Aes

10.1 Adverse Events

10.1.1 Definition of AE

An AE is defined as any untoward medical occurrence in the process of the clinical study, regardless of its relationship to the investigational medical device.

10.1.2 Classification of adverse events

Mild: The subject can tolerate, without effecting the treatment. No special treatment is required. There is no impact on the health of the subject.

Moderate: The subject cannot tolerate, with the need of device removal or special treatment. There is direct impact on the health of the subject.

Severe: It endangers a subject's life, leading to disability or death. Device removal or an emergency treatment needs to be done immediately.

10.1.3 Correlation between Aes and investigational devices

- 1) Definitely related: The type of Aes has been confirmed as the type of reaction that must occur in investigational medical device, which accords with the reasonable chronological order after treatment, and this AE cannot be explained by other reasons.
- 2) Probably related: The occurrence of Aes may be caused by the use of investigational medical device, and there is a reasonable chronological order between the occurrence of events and the use of investigational medical device.
- 3) Possibly related: The occurrence of Aes may be caused by the investigational medical device, and other factors cannot be ruled out. There is a reasonable chronological order between the occurrence of Aes and the use of investigational medical device, and the causality between the events and the use of investigational medical device cannot be ruled out.
- 4) Possibly unrelated: The occurrence of Aes is more likely related to other factors. Or the occurrence time of the AE indicates that it is unlikely to have causality with the use of investigational medical device.
- 5) Not related: There is no correlation between the occurrence of Aes and the use of investigational medical device.
- 6) Unable to determine: The correlation between the occurrence of Aes and the use of investigational medical device cannot be determined.

10.2 SAEs

SAEs are the following events occurred during the clinical study:

- 1) Death;
- 2) Fatal disease or injury;
- 3) Permanent impairment of a body structure or a body function;
- 4) Resulting in hospitalization or prolonged hospitalization;
- 5) Medical or operative intervention is required to avoid any permanent impairment in the physical structure or physical function;
- 6) Fetal distress, fetal death or congenital anomalies, congenital defect, etc.

11.2 Study monitoring The Sponsor's representatives or its designated personnel are allowed to visit the study site regularly, to assess the quality of data and the integrity of study. The representative will review the study records of the study site and directly compare these records with the original documents, discuss the implementation of the study with the investigators, and confirm the rationality of study implementation. In addition, the study can be evaluated by internal auditors of the Sponsor and government inspectors who must be allowed to view eCRFs, original documents, and other study documents. The Sponsor's audit report will be kept confidential.

During the monitoring visit, the investigator or the designated personnel under the investigator must be present at some times to review the data, answer any queries, and be allowed to directly access to subject records (such as medical records, office documents, hospital documents, and study-related documents) for validation of original data. Before each visit, the eCRF must be filled in and provided to the Sponsor's representative for checking its accuracy and integrity.

11.3 CRF and study records: All records will be kept confidential. Personal information of subjects, including names, shall not be disclosed at any time. Subjects' clinical/experimental data shall not be disclosed to any party other than the Sponsor

or its designated personnel and relevant competent government agencies. In all cases, the information must be kept confidential with caution for subjects. In the eCRF and other study-related documents, the number will be used to represent the subject's identity.

The study site staff will collect data electronically. Initially, data will be collected on the original documents, and then transcribed to the eCRF. The eCRFs will not be used as the primary medium for collecting any data. The data in eCRF is sourced from original documents, and must be consistent with original documents. Any deviation between eCRF and original documents must be explained and recorded. All necessary information must be recorded in the blank space provided in the eCRF. If certain data are not available or not applicable, they must be recorded as Not Available or Not Applicable; no blank space can be left.

Each subject participating in the study must have a complete eCRF, and each page in the form must be reviewed and approved by the PI. The PI will confirm that he/she has reviewed the recorded data by electronic signature in the electronic data collection page. The PI may entrust the review and confirmation to a qualified doctor who may be appointed as an assistant investigator. Investigators must keep a copy of the eCRF, including records of changes and corrections.

11.4 Data and Safety Monitoring Board: An independent Data and Safety Monitoring Board (DSMB) will be established to regularly review and analyze all safety data. The effect data generated by the study will be evaluated by DSMB for potential risks and benefits of the treatment. DSMB will be composed of independent professional doctors (at least 2 persons) who will not undertake the recruitment of subjects in this study and a biostatistician whose identity is not disclosed. DSMB will keep SAEs under review. DSMB will review the frequency and severity of all aEs as well as demographic data, etc. Specific meetings may be held for any safety reasons during the study. Based on results of data review, if any termination criterion is met, DSMB will give suggestions on whether to continue, adjust or terminate the study. Other responsibilities and details of DSMB will be included in the DSMB Charter.

11.5 Clinical Event Committee (CEC): The CEC will independently and impartially evaluate the safety events, including at least all protocol-specified safety endpoints of the subjects. The CEC should be composed of at least three independent physicians, one of whom will act as CEC President. Details regarding the responsibilities of CEC

members and clinical events that require CEC review will be included in the CEC constitution.

- 11.6 **Imaging assessment committee (IAC):** The primary and secondary endpoints of the trial involve quantitative imaging assessments, which will be reviewed by the IAC with data including at least: CT/MRI (screening period/baseline, 90-day follow up [V4], 360-day follow up [V5]), and DSA imaging (target vessels [MMA main and branch vessels]).
- 11.7 **Outcome Assessment Committee (OAC):** The OAC is responsible for evaluation of multiple subjective data, including at least clinical symptoms and mRS score (90-day follow up [V4] and 360-day follow up [V5]).

Appendix 1. Study Flowchart

Study procedure	Screening period ^a	Baseline	Follow-up period			
			V0	V1	V2	V3
Visit time ^b	Day -14 to Day 0	Day 0		Discharge	Day 30	Day 90
Informed consent	X					
Demographic data	X					
Inclusion/exclusion criteria		X				
Medical history and previous medication	X					
Vital signs	X			X	X	X
Admission examination ^c	X					
CT/MRI ^d	X				X	X
DSA ^e		X				
Randomization and treatment		X				
Total hospitalization expenses			X		X	X
Efficacy endpoints					X	X
SAEs					X	
SDH-related death events					X	
Severe surgery-related complications					X	
Concomitant medication/treatment			X	X	X	X
mRS score	X				X	X
EQ-5D scale	X				X	X

^a Screening visit and baseline visit can be conducted on the same day

^b The visit time window is ± 7 days for V3, ± 14 days for V4, and ± 30 days for V5

^c Blood routine (red blood cell count, white blood cell count, platelet count, hemoglobin), coagulation (APTT, INR), hepatic and renal function (ALT, AST, BUN, Cr), electrolytes (potassium, sodium, chlorine), random blood glucose; urine HCG test is required for female of child-bearing potential

^d CT is mandatory and MRI is optional. The doctor should decide whether MRI is necessary based on the condition of the patient

^e This item is conducted only in MMA embolization group

Appendix 2. EQ-5D Scale

Your name:

By placing a tick "√" in **one** box in each group below, please indicate which statements best describe your own health status **today**.

Mobility

I have no problems in walking about (1 point)

I have slight problems in walking about (2 points)

I have moderate problems in walking about (3 points)

I have severe problems in walking about (4 points)

I am unable to walk about (5 points)

Self-care

I have no problems washing or dressing myself (1 point)

I have slight problems washing or dressing myself (2 points)

I have moderate problems washing or dressing myself (3 points)

I have severe problems washing or dressing myself (4 points)

I am unable to wash or dress myself (5 points)

Usual Activities (e.g., work, study, housework, family or leisure activities)

I have no problems doing my usual activities (1 point)

I have slight problems doing my usual activities (2 points)

I have moderate problems doing my usual activities (3 points)

I have severe problems doing my usual activities (4 points)

I am unable to do my usual activities (5 point)

Pain /Discomfort

I have no pain or discomfort (1 point)

I have slight pain or discomfort (2 points)

I have moderate pain or discomfort (3 points)

I have severe pain or discomfort (4 points)

I have extreme pain or discomfort (5 points)

Anxiety or Depression

I am not anxious or depressed (1 point)

I am slightly anxious or depressed (2 points)

I am moderately anxious or depressed (3 points)

I am severely anxious or depressed (4 points)

I am extremely anxious or depressed (5 points)

Please mark the point that best represents your health today:

100 means the best health you can imagine

0 means the worst health you can imagine

The best health you
can imagine

100

90

80

70

60

50

40

30

20

10

0

The worst health
you can imagine

Appendix 3. Modified Rankin Scale (mRS score)

Patient symptoms	Score
No symptoms	0
No significant disability despite symptoms; able to carry out all usual works and live	1
Slight disability, unable to carry out all previous activities, but able to look after own affairs without assistance	2
Moderate disability; requiring some help, but able to walk without assistance	3
Moderately severe disability; unable to walk without assistance and unable to attend to own bodily needs without assistance	4
Severe disability; bedridden, incontinent and requiring constant nursing care and attention	5

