## 8.2. Specifications of Primary Efficacy Endpoints Analyses

### 8.2.1. Definitions and Derivations

- **Symptomatic** SDH recurrence (in the trepanation/drainage group) refers to a situation in which the maximum thickness of hematoma of patients exceeds 10 mm, combined with neurological symptoms, or the need for repeat surgery.
- Symptomatic SDH progression (in the non-trepanation/drainage group) refers to a situation in which the maximum thickness of increases by more than 3 mm compared with baseline, combined with neurological symptoms, or the need for surgery.
- The results of central imaging evaluation and analysis of CT/MRI examinations required for the determination of the subject 's primary endpoint in this study will be presented in tables and listings, respectively. Central image evaluation will be performed by the independent Core Lab. Evaluation of neurological symptoms will be derived from the Outcome Assessment Committee (OAC) review data.
- It should be noted that if there is a record of reoperation in participants who have undergone trepanation/drainage, and there is a record of surgical treatment in subjects who have received medical therapy without trepanation/drainage, the occurrence of the primary endpoint can be directly determined, and hematoma thickness or neurological symptoms are no longer required.
- In case of non-negligible amounts of missing data (>5%), we will use the MCMC method based on the Missing at random (MAR) assumption to impute missing data. The regression model will include group, sex, age, BMI, baseline mRS score and baseline maximum

hematoma thickness. The number of imputations is 10, seed=1234, nbiter=200. SAS code examples for multiple imputation will be provided in Appendix 3.

- Hematoma recurrence (trepanation/drainage group) or symptomatic hematoma progression (non-surgical group) at day 90 will be analyzed as follows. If there is any discrepancy between EDC and central imaging assessment scan date in the determination of visit window, the date determined by central imaging assessment shall prevail.

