**Table 5. Data Handling Rules for Primary Endpoint Analysis**

Analyses	Death within 104 days (90 days + 14 days)	Visit out of window	No 90-day (<math>\pm</math> 14 days) visit data
Primary analyses	As if an event occurred	Observed measurements for out-of-window visits will be treated as 90-day results	Multiple imputation*
Sensitivity Analyses1	As if an event occurred	As No Event	As if an event occurred
Sensitivity Analyses 2	As if an event occurred	As No Event	As No Event

\*If percentage of missing primary endpoint is less than 5%, multiple imputation will not be performed and missing data will be regarded as no event.

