## 9.1.2. Specifications of Secondary Efficacy Endpoint Analyses

### 9.1.2.1. Definitions and Derivations

- Change from 90 days/360 days post study treatment will be calculated as 90 days/360 days measurement – baseline measurement
- Total days in hospital = Date of discharge - Date of hospitalization + 1 (Hospital information page)
- Other definitions and derivations are the same as in Section 8 .2.1

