### 9.1.2.2. Statistical Analysis Methods

- 360 days recurrence or progression of SDH after randomization will be analyzed in the same way as the primary endpoint (Section8.2.2)
- Ordinal logistic regression will be used for intergroup comparison of mRS scale scores at 90 and 360 days after randomization, with treatment group, sex, age, surgical treatment strata (trepanation/drainage vs. no trepanation/drainage), any usage of antiplatelet or anticoagulant therapy within one month before randomization(yes vs no), hematoma volume of baseline CT as covariates.
- Other categorical secondary endpoints will be analyzed in the same way as the primary endpoint **(Error! Reference source not found.Error! Reference source not found.Section)**

- The linear mixed effects model approach will be used to estimate the mean estimate (95% CI) and the mean estimate (95% CI) of the differences between groups as well as the P values of the differences between groups for the change in maximum hematoma thickness at 90 days after randomization compared to baseline and the change in hematoma volume at 90 days after randomization compared to baseline; Treatment group variables, sex, age, surgical treatment strata (trepanation/drainage vs. no trepanation/drainage), any usage of antiplatelet or anticoagulant therapy within one month before randomization(yes vs no), hematoma volume of baseline CT , visit variables, and visit by treatment group variable interactions will be included in the model and site as the random effect.
- For other continuous secondary endpoints, T tests will be used to compare groups, and 95% confidence intervals for the difference in means between groups will be calculated using normal approximation.

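### Death has no place on the trial's mRS, and the only death rule available for the 360-day recurrence/progression endpoint stops at day 104

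*Protocol*

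**What the plan says.** **mRS.** Protocol Appendix 3 lists grades 0 to 5. The last is "Severe disability; bedridden, incontinent and requiring constant nursing care and attention", and no grade or note covers death. SAP 9.1.2.2 states: "Ordinal logistic regression will be used for intergroup comparison of mRS scale scores at 90 and 360 days after randomization". SAP 9.1.2.1 defines change as the follow-up measurement minus the baseline measurement. Neither says what to do with a patient who died before the visit. Protocol 7.1.4 says that missing values are not imputed. SAP 9.1.2.1, however, refers secondary endpoints back to the primary endpoint's section: "Other definitions and derivations are the same as in Section 8 .2.1".

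**360-day recurrence/progression.** SAP 9.1.2.2 states: "360 days recurrence or progression of SDH after randomization will be analyzed in the same way as the primary endpoint". SAP Table 6 sends this endpoint to Table 4, where death is listed with a 104-day limit. In Table 5 the death column is headed "Death within 104 days (90 days + 14 days", and such deaths count as events. SAP Appendix 3 repeats the table with the same limit. For patients without visit data, Table 5 gives multiple imputation in the main analysis. If under 5% of primary outcomes are missing, "missing data will be regarded as no event". Sensitivity Analysis 1 scores a missing visit as an event and Sensitivity Analysis 2 as no event.

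**Related text.** Protocol 7.3.1 counts death from any cause within 90 days as a primary event. SAP Appendix 1 gives the 360-day visit a window of ±30 days. SAP Appendix 2 keeps missing observations in the denominator of percentages unless otherwise stated. SAP 1.2 and Table 7 report all-cause death to 90 and 360 days as a safety outcome.

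**The concern.** Functional outcome and 360-day recurrence/progression are the endpoints meant to show whether any early benefit lasts. A death has no mRS measurement, so unless a rule supplies one, the ordinal and change analyses compare survivors only, and the comparison is no longer between the groups as randomized. If imputation supplies a value, it is drawn from grades 0 to 5, and the worst possible outcome is recorded as some degree of living function. Either way, the arm with more deaths is not charged for them in these analyses.

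For the 360-day endpoint the question is whether it is still the same composite as the 90-day one. At 90 days any death is an event. At 360 days, read literally, a death up to day 104 is an event, while an event-free death on, say, day 200 is a missing visit. One label would then cover two definitions. The SAP's Table 1 also removes time-to-event analysis for the secondary endpoints, so no planned survival analysis would pick up the late deaths.

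**Working it through.** **1. The plan's own figure.** Inputs from Protocol 7.1.3: 12% versus 5%, two-sided 5%, power 90%, loss 8%. The pooled two-proportion formula without continuity correction gives 332 per arm. Then 332/(1 − 0.08) = 360.9, so 361 per arm and 722 in total. This reproduces the stated size. Nothing below changes it.

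**2. Which missing-data branch applies.** 5% of 722 = 36.1 patients; 8% of 722 = 57.8. At the planned loss the imputation branch applies: "In case of non-negligible amounts of missing data (>5%), we will use the MCMC method". With better follow-up than planned, the no-event branch applies. The imputation model in SAP 8.2.1 contains group, sex, age, BMI, baseline mRS and baseline maximum hematoma thickness. It has no indicator for death, so a dead patient is treated like a living one with the same baseline.

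**3. 360-day endpoint.** Assumptions: 12% versus 5% recurrence/progression at 360 days, 361 per arm, and late deaths (after day 104) only in patients with no earlier event. Late mortality of 1% to 4% is 3.6 to 14.4 patients per arm. Scored as no event, the rates stay at 12% and 5%. Scored as events, each rate rises by its late mortality. Simple within-arm imputation applies the rate seen in the others: for 2% control and 4% embolization, 0.12/0.98 = 12.2% and 0.05/0.96 = 5.2%.

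| Late deaths, control / embolization | Difference, no event | Difference, imputed | Rates if events | Difference if events | Power if events |
|---|---|---|---|---|---|
| 1% / 1% | 7.0 | 7.1 | 13% / 6% | 7.0 | 0.90 |
| 4% / 4% | 7.0 | 7.3 | 16% / 9% | 7.0 | 0.81 |
| 2% / 4% | 7.0 | 7.0 | 14% / 9% | 5.0 | 0.56 |
| 4% / 2% | 7.0 | 7.4 | 16% / 7% | 9.0 | 0.97 |

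Differences are in percentage points. Power with no late deaths counted is 0.92. Unequal late mortality thus moves the difference by 2 points in either direction if deaths count, and hardly at all if they do not.

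**4. Ordinal mRS.** Assumptions: survivors in both arms share the distribution 45/27/12/8/5/3% over grades 0 to 5, and death, where counted, is a seventh and worst category. A proportional-odds fit gives these odds ratios for worse outcome, embolization versus control:

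| Deaths, control / embolization | Deaths omitted | Death as worst category |
|---|---|---|
| 6% / 3% | 1.00 | 0.905 |
| 3% / 6% | 1.00 | 1.105 |

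A second assumed distribution (40/30/15/8/5/2%) gives 1.07 at 2% / 4%, 1.14 at 2% / 6% and 0.88 at 6% / 2%, again with 1.00 when deaths are omitted.

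**5. Scale against noise.** With 361 per arm the standard error of the log odds ratio is about 0.14. Since ln(0.905) = −0.10, the shift is about 0.10/0.14 = 0.7 standard errors, and that is with mortality twice as high in one arm.

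**The case against.** The strongest objection concerns the 360-day endpoint. Table 5 is titled for the primary endpoint. To send a day-200 death to imputation, one must read its column on missing 90-day visits as if it concerned the 360-day visit, while leaving the neighbouring death column at day 104. Carried over consistently, with the ±30-day window, the table would give death within 390 days as an event. This stands in part. A sensible programmer might do exactly that, but no text says so, and the 104-day limit is the only one written, in three tables.

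Safeguards also exist. The two sensitivity analyses score missing visits both ways, so they bracket the handling of late deaths, though they treat living dropouts in the same way and do not isolate death. A late death after a recorded recurrence or operation is still an event. All-cause mortality to 360 days is reported separately, so an imbalance in deaths could not be hidden. Protocol 7.3.1 also ties the death rule to the 90-day primary endpoint only, so counting late deaths is a choice of estimand, and step 3 shows that it costs power when late mortality is equal.

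On mRS, the SAP is silent; it does not order deaths to be excluded. A table row lost when the text was extracted cannot be fully ruled out, but Appendix 3 reads as complete and no other section scores death.

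A reader might go further and infer that a death would count as a good outcome for mRS 0 to 2 or 0 to 3, because secondary endpoints inherit a table in which death is an event. The documents do not support this. The event in Table 5 is hematoma recurrence or progression, not a favourable mRS. Under SAP Appendix 2 a dead patient with no mRS stays in the denominator and is not counted as meeting the threshold. Those two proportions are therefore largely protected.

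**Conclusion.** The point holds for two sets of secondary analyses. In the ordinal and change analyses of mRS, death is not represented as an outcome, whether deaths are omitted or imputed. For the 360-day recurrence/progression endpoint the death window is unwritten, and the literal reading makes the main analysis a different composite from the 90-day one.

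The sizes rest wholly on assumed mortality and, for mRS, on an assumed survivor distribution. In the examples the mRS odds ratio moves from 1.00 to about 0.91 or 1.10, and the 360-day difference moves by 2 points if all late deaths fall in event-free patients. It would be wrong to infer that the plan favours embolization: the direction depends on which arm has more deaths, and the documents do not say. That uncertainty is the reason to settle the rule before outcomes are seen. The 90-day primary analysis and N = 722 are untouched, so this should be corrected but does not threaten the main conclusion.

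**What to change.** 1. In SAP 9.1.2.1, score patients who are dead by the visit as mRS 6, the worst category, in the ordinal and change analyses, and add that category to Protocol Appendix 3.
2. In the same section, confirm that these patients count as not meeting mRS 0 to 2 or 0 to 3.
3. Add a 360-day row to SAP Table 5 and its copy in SAP Appendix 3: death within 390 days (360 + 30) is an event, and imputation or no-event scoring applies only to patients not known to have died.
4. Report the hematoma-only component of the 360-day endpoint beside the composite, because equal late deaths in both arms would dilute the contrast.

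The cost is a few lines of SAP text and one line in the protocol appendix. Deaths to 360 days are already collected for the safety analysis, so no new data and no patient burden are involved. The downside is the loss of power shown in step 3, from 0.92 to 0.90 at 1% late mortality in each arm and to 0.81 at 4%.
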